Treatment will be administered until unacceptable toxicity, loss of clinical benefit, disease progression or completion of 2 years of therapy. If the patient has benefit after 2 years, the trial chair and the sponsor must be consulted to evaluate how to continue with the treatment.

If pseudoprogression is suspected, patients can continue with the study therapy until loss of clinical benefit as judged by the principal investigator. Prior to continuing with the study therapy, the trial chair of the study must be informed.

Statistical considerations:

This study is designed to show that experimental treatment will achieve a median PFS of 4.5 months (expected median for standard scheme is 3 months which is equivalent to consider an improvement of 0.66 in terms of hazard ratio), with a statistical power of 90% and a one-sided type I error of 10%. On these bases and considering Lachin design, 45 pts are needed (44 or more events for null hypothesis and 43 or less events for alternative hypothesis) over a period of 18 months with a minimum median follow-up of 12 months to perform an exponential test. Considering a 5 % of drop-out patients and a hazard of 0.04 for dropouts a total sample size of 47 patients will be needed. In

case of having 43 or less events during follow-up alternative hypothesis will be concluded and experimental treatment will be declared as promising.

The expected accrual rate is 2 patients per month for the first 6 months, increasing to 4-5 patients per month thereafter. Primary analysis is expected to be available 18 months after the inclusion of the first patient. In order to reach the proposed sample size, if a patient initially enrolled in the study does not fulfil the inclusion criteria, they will be replaced by a new one subject that fulfil them, this replacement will ensure that the sample size will be the one calculated initially.

Total trial duration: 3.5 years (1.5 years of recruitment, approximately 2 years of treatment and 1 month for the safety follow up)

Translational research:

Blood samples, tumor biopsy and malignant pleural effusion will be collected prior to initiating M7824 and when possible at tumor progression for the correlative studies.

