4.3. Exploratory objectives

- To correlate efficacy endpoints (PFS and ORR) with PD-L1 expression. This will be measured by PD-L1 immunohistochemistry in the central laboratory.
- To correlate efficacy endpoints (PFS and ORR) with activation of TGF-β pathway in tumor biopsies obtained at baseline and at tumor progression. This will be measured by SMAD2/3 and phospho-SMAD2/3 immunohistochemistry in tumor biopsies obtained at baseline and at tumor progression.
- To correlate efficacy endpoints (PFS and ORR) with TGF-β levels along with additional cytokines measured in serum obtained prior to initiation of immunotherapy and cytokines at tumor progression.
- To correlate efficacy endpoints (PFS and ORR) with TGF-β levels along with additional cytokines in pleural effusion obtained prior to initiation of immunotherapy and at tumor progression. To determine the immune cell subpopulations harvested in the pleural effusion at baseline and at tumor progression using flux cytometry in a subset of patients included in the study.
- To determine the predictive value of the immune groups based on the expression of cytotoxic T cells and Th2 cells signature measured in the tumor sample at baseline by using gene expression panels from NanoString technologies.

5. Trial design, duration and termination

[figure not shown]
This is an open-label, non-randomized, phase II, single arm, multi-center clinical trial.

Patients enrolled in the study will receive treatment with M7824 that will be administered at day 1 and day 14 or (2 weeks \pm 3 days) of 28 days cycle. Cycles will be administered until unacceptable toxicity, loss of clinical benefit, disease progression or completion of 2 years of therapy. If the patient has benefit after 2 years, the trial chair and the sponsor must be consulted to evaluate how to continue with the treatment.

Patient accrual is expected to be completed within 1.5 years excluding a run-in-period of 4-6 months. Treatment and follow-up are expected to extend the study duration to a total of 3.5 years. Patients will carry out a safety follow-up 1 month after the end of treatment independently of the cause of end of treatment. The study will end once safety follow-up has concluded.

The trial will end with the preparation of the final report, scheduled for 4.5 years after the inclusion of the first patient approximately.

Study schema:

6. Patient selection

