4. Adverse events: Changes from baseline abnormalities (new or worsened clinically significant ones) should be recorded as adverse events on the Adverse Event eCRF until this visit. For laboratory parameters, only grade 2 events will be reported as an AE. All the other events not related to laboratory values will be reported from grade 1. SAEs and AESIs must be recorded and followed from the subject written informed consent signature to 30 days from last dose of treatment.
5. Concomitant medications: Changes from baseline should be recorded on the eCRF until this visit (30 days from last dose of treatment).
6. Tumor assessment: if the end of treatment reason is other than disease progression the CT SCAN schedule will be performed every 8 weeks:

- a. **Chest and abdomen CT SCAN** with oral/IV contrast (unless contraindicated) to determine measurable disease according to mRECIST v1.1.

It is not mandatory to perform the tumor assessment in first follow up visit if the end of treatment reason is other than progression disease and a tumor assessment has been performed in the previous 8 weeks.

After the safety follow up visit, all the patients will be followed by a telephone call every 3 months until the end of study participation or last patient last visit.

End of study participation of the patients included in the study will be the date of the last study assessment.

9. Investigational Medicinal Product

Bintrafusp alfa (M7824) is the Investigational Medicinal Products (IMP) used in this trial. Merck will provide the IMPs at no cost for this trial.

Complete details of the trial drug logistics, distribution, packaging, labelling, storage and handling as well as accountability are described in the **BIMES drug supply manual** that will be provided in the Pharmacy site file to all the participant sites.

Description of the Investigational Medicinal Products

Bintralusp alfa (M7824) is a bifunctional fusion protein composed of the extracellular domain of the transforming growth factor β (TGF- β) receptor II (a TGF- β "trap") fused to a human immunoglobulin G1 antibody blocking programmed death-ligand 1 (PD-L1).

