This study is designed to show that experimental treatment will achieve a median PFS of 4.5 months (expected median for standard scheme is 3 months which is equivalent to consider an improvement of 0.66 in terms of hazard ratio), with a statistical power of 90% and a one-sided type I error of 10%. On these bases and considering Lachin design, 45 pts are needed (44 or more events for null hypothesis and 43 or less events for alternative hypothesis) over a period of 18 months with a minimum median follow-up of 12 months to perform an exponential test. Considering a 5 % of drop-out patients and a hazard of 0.04 for dropouts a total sample size of 47 patients will be needed. In case of having 43 or less events during follow-up alternative hypothesis will be concluded and experimental treatment will be declared as promising.

The expected accrual rate is 2 patients per month for the first 6 months, increasing to 4-5 patients per month thereafter. Primary analysis is expected to be available 18 months after the inclusion of the first patient.

In order to reach the proposed sample size, if a patient initially enrolled in the study does not fulfil the inclusion criteria, they will be replaced by a new one subject that fulfil them, this replacement will ensure that the sample size will be the one calculated initially.

Reference: Lachin, John M (2000). Biostatistical Methods: The assessment of Relative Risks. John Wiley & Sons, New York, NY.

17. Criteria for termination of the trial

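### The forecast of a primary analysis at month 18 cannot be met together with the 12-month minimum median follow-up at the plan's own accrual, and no data cut-off is defined

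*Combined protocol and SAP*

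**What the plan says.** The statistical considerations in Section 1 (Protocol summary) and Section 16 carry the same text. The design is sized "over a period of 18 months with a minimum median follow-up of 12 months to perform an exponential test". The 18 months is not labelled as an accrual period or a total period. The accrual assumption is "The expected accrual rate is 2 patients per month for the first 6 months, increasing to 4-5 patients per month thereafter". The timing statement is "Primary analysis is expected to be available 18 months after the inclusion of the first patient".

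On recruitment, Section 1 gives "Total trial duration: 3.5 years (1.5 years of recruitment, approximately 2 years of treatment", and Section 5 says "Patient accrual is expected to be completed within 1.5 years excluding a run-in-period of 4-6 months".

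The decision rule is a count: "In case of having 43 or less events during follow-up alternative hypothesis will be concluded", with 44 or more events pointing to the null. The step from 45 to 47 patients is explained by "Considering a 5 % of drop-out patients and a hazard of 0.04 for dropouts", with no time unit for the hazard.

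Neither section defines the data cut-off for the primary analysis.

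**The concern.** The only date given for the primary analysis conflicts with the only follow-up condition given for it. For a 12-month median at month 18, the 24th of 47 patients must have entered by month 6. The plan expects 12 patients by then, so no later accrual rate can close the gap.

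Two things are at stake. Cutting at month 18 removes follow-up that the stated power relies on. Also, a rule that counts events without reference to person-time gives a different answer at each cut-off date. Leaving the date open in an open-label trial with investigator-assessed PFS leaves a choice that the plan should have closed.

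**Working it through.** **Inputs (Sections 1 and 16).** N = 47 (45 before dropout); null median 3 months and alternative 4.5 months; one-sided 10% error and 90% power; accrual as quoted. Hazards are l0 = ln2/3 and l1 = ln2/4.5 per month. Assumptions: exponential PFS, entry taken as first dose, and each patient entering at the midpoint of its accrual interval.

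**1. The plan's own sample size.** In the log-hazard form, N = [(z_a/√p0 + z_b/√p1)/ln(l0/l1)]², with z_a = z_b = 1.2816.
- If every patient has 12 months of follow-up, p0 = 1 − 2^(−12/3) = 0.9375 and p1 = 1 − 2^(−12/4.5) = 0.8425. This gives N = 45.0 (45.7 in the hazard form), against 45 stated.
- With 18 months of accrual plus 12 months of follow-up, the hazard form gives N = 42.4. On that reading 45 patients yield 44.3 expected events under the null and 42.6 under the alternative, close to the stated 44 and 43.
- Dropout: 45/0.95 = 47.4, against 47.

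So the design basis is recoverable but not unique, and the 18 months could mean either period.

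**2. Follow-up at month 18.** Median entry month = 6 + (47/2 − 12)/rate. Median potential follow-up at month 18 is 18 minus that entry month, and the 12-month median falls at 12 plus it.

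| Rate after month 6 | Median entry (month) | Median follow-up at month 18 | 12-month median reached |
|---|---|---|---|
| 4/month | 6 + 11.5/4 = 8.9 | 9.1 months | month 20.9 |
| 4.5/month | 6 + 11.5/4.5 = 8.6 | 9.4 months | month 20.6 |
| 5/month | 6 + 11.5/5 = 8.3 | 9.7 months | month 20.3 |

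- Other entry conventions give 9.0-10.1 months at month 18.
- Even accrual over 1.5 years gives 18 − 9 = 9.0 months at month 18, and 12 months at month 21.
- If the 4-6 month run-in counts from the first patient (22-24 months of even accrual), only 35-38 of 47 are enrolled at month 18 and the 12-month median falls at month 23-24.

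**3. Power of the exponential test.** With f the potential follow-up and g the dropout hazard, each patient's event probability is l/(l+g)·(1 − exp(−(l+g)f)); p0 and p1 are the means over patients. Then z_b = [√n·ln(l0/l1) − z_a/√p0]·√p1 on the log scale, or z_b = [√n(l0 − l1) − z_a·l0/√p0]/(l1/√p1) on the hazard scale.

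Example on the log scale, 4/month, no dropout:
- Month 18: p0 = 0.841, p1 = 0.726; z_b = (2.780 − 1.398) × 0.852 = 1.18, power 88.0%.
- Month 20.9: p0 = 0.918, p1 = 0.824; z_b = (2.780 − 1.338) × 0.908 = 1.31, power 90.5%.

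Ranges over 4-5/month and both scales:

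| Cut-off | No dropout or 0.04/year | 0.04/month |
|---|---|---|
| Month 18 | 86.8-89.1% | 83.1-85.9% |
| 12-month median (month 20.3-20.9) | 89.8-90.7% | 85.9-87.3% |
| Even accrual, month 18 | 83.7-85.7% | not tabulated |
| Even accrual, month 21 | 88.6-89.5% | not tabulated |

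Comparing like with like, the timing loss is 1.6-3.0 points with no dropout or 0.04/year. Simulation of the test on events and person-time gives 86.5-88.1% at month 18 and 89.1-89.7% at the 12-month median (no dropout or 0.04/year).

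**4. The count rule taken literally.** Probability of 43 or fewer events, summing the 47 individual event probabilities exactly; ranges cover 4-5/month:

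| Cut-off | True median 3 months, no dropout | True median 3 months, 0.04/year | True median 4.5 months, no dropout or 0.04/year |
|---|---|---|---|
| Month 18 | 86-96% | 90-97% | above 99% |
| 12-month median | 46-55% | 57-65% | 97-99% |
| Last patient at 12 months (month 24.9-26.6) | 1.8-3.0% | 7.8-10.2% | 45-69% |

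The third and fourth columns show that when the rule's error falls to about 10% or less, its power has fallen well below 90%.

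**The case against.** The strongest reply is that month 18 is only an expectation, whereas the follow-up clause sets a minimum. Followed as written, the minimum prevails and the analysis simply slips by two to three months. That is a fair reading, and it stands as far as it goes. A reader might infer that the plan mandates an under-powered analysis at month 18, and the documents do not say that. What remains is that the two statements cannot both be met, and no cut-off is written that would settle which one yields.

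Second, the timing effect is small, and the large false-positive figures belong mainly to the count rule. That also stands. A reader might infer that the trial carries an 86-96% type I error. Those figures hold only if the count rule is applied literally at month 18 without dropout, and the same paragraph names an exponential test. They are relevant here because they show how strongly the date governs the answer.

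Third, a reader might infer either that a later date repairs the count rule or that no date can bring its error down. Neither is right. Waiting until the last patient has 12 months brings the error to about 2-10% with no dropout or 0.04/year, but power is then about 45-69%.

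Fourth, power below 90% is not due to month 18 alone. Even accrual gives 88.6-89.5% at month 21, and using 45 patients instead of 47 gives 88.7-89.8% at the 12-month median with no dropout or 0.04/year. This stands, and it is why power should be restated and not assumed.

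**Conclusion.** The inconsistency is certain. At the stated accrual, month 18 gives 9.1-9.7 months of median potential follow-up and not 12. The 12-month median arrives at about month 20.3-20.9, or month 21 with even recruitment over 1.5 years. No accrual reading in Sections 1, 5 or 16 reaches it by month 18. Potential follow-up without dropout is the most generous definition; counting dropout would shorten it.

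On power the effect is modest: about 87-89% in place of 90%, with no dropout or 0.04/year. The larger consequence is that the undefined cut-off decides the outcome of the written count rule. None of the three dates examined gives both 10% error and 90% power under that rule.

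The figures rest on exponential PFS, 47 patients, entry equal to first dose, and a dropout hazard whose unit the plan does not state. Severity is minor to moderate.

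**What to change.** In Sections 1 and 16:

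1. State whether the 18 months is the accrual period or the total period, and whether 12 months was meant as a median or for every patient.
2. Define the primary data cut-off as the date when enrolment is complete and median potential follow-up has reached at least 12 months. Give the start point for patients who are registered but never dosed, since the ITT population in Section 16 rests on registration while PFS runs from first dose.
3. Replace the 18-month forecast with the date this implies: about month 20-21 at the stated accrual, and later if the run-in counts from the first patient or if 12 months for every patient was intended.
4. State that the decision is made by the one-sided 10% exponential test on events and person-time, not by the raw event count.
5. Give the unit of the 0.04 dropout hazard and restate power at the cut-off. With 47 patients this is about 90% at planned accrual with no dropout or 0.04/year, 88.6-89.5% with even 18-month accrual, and about 86-87% at planned accrual if 0.04 is per month.

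**Cost.** Readout comes about 2-3 months later, within the 3.5-year study, and the stated power may have to be slightly lower. No extra patients, scans or visits are needed: Section 8.1.5 already provides that "if the end of treatment reason is other than disease progression the CT SCAN schedule will be performed every 8 weeks". Item 4 changes the written decision criterion, so it is more than an editorial edit and should be settled before outcome data are reviewed.

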17.1. General criteria for termination of the trial

The trial may be discontinued early in parts or completely if the information on the product leads to doubt as to the benefit/risk ratio, by decision of Fundación GECP or Trial Steering Committee, or at the suggestion of the IDMC.

The trial can be terminated at any time if the authorization and approval to conduct the study is withdrawn by ethics committee or regulatory authority decision, insufficient accrual, emerging new data impacting the scientific value of the trial or on ethical grounds.

17.2. Discontinuation of protocol treatment and from the study for individual patients

Patients may be withdrawn from the protocol treatment and from the study in the following situations:

- Occurrence of unacceptable toxicities. Stopping protocol treatment is determined by medical judgment of the treating physician.
- Disease progression per investigator assessment according to mRECIST v1.1 and loss of clinical benefit
- Symptomatic deterioration attributed to clinical disease progression
- Intercurrent severe illnesses which would in the judgment of the investigator affect assessments of the clinical status to a significant degree and require discontinuation of protocol therapy
- Request by the patient. Patients have the right to refuse further trial treatment at any time during the trial. Such patients will remain in the trial and will be transferred to the follow-up phase.
- If a patient refuses to have follow-up examinations and tests needed to determine whether the treatment is safe and effective
- Protocol non-compliance or study termination by sponsor or site closure by the sponsor (poor protocol adherence, inaccurate or incomplete data recording...)

- Pregnancy
- Patient non-compliance, defined as a failure to comply with the protocol requirements as determined by the protocol

The decision for discontinuation of protocol treatment and the study of individual patients is taken by the treating physician based on his medical evaluation and taking into consideration the patient's individual situation. Specific reasons for trial discontinuation in which further collection of data is not allowed are: withdrawal of consent, patient lost to follow up, death.

All possible measures will be undertaken to maintain the investigation program and to continue the follow-up even if the treatment was prematurely concluded and/or if the patient did not attend the follow-up visits at the participating institution.

The primary reason for the treatment and study discontinuation should be documented on the appropriate eCRF.

18. Ethics aspects, regulatory approval, and Patient Informed Consent

The Investigator will ensure that this study is conducted in full conformance with the principles of the "Declaration of Helsinki" or with the laws and regulations of the country in which the research is conducted, whichever affords the greater protection to the individual. The study must fully adhere to the principles outlined in "Guideline for Good Clinical Practice" ICH6 Tripartite Guideline (January 1997) or local Spanish law if it affords greater protection to the patient. For studies conducted in the EU/EEA countries, the Investigator will ensure compliance with the EU Clinical Trial Directive (2001/20/EC).

18.1. Ethical Review Board/Ethics Committee/Health Authority

All protocols and the patient informed consent forms must have the approval of a properly constituted committee or committees responsible for approving clinical trials. The Ethic Committee decision must contain approval of the designated investigator, the protocol (identifying protocol title and version number), and of the patient informed consent.

The Ethic Committee written, signed approval letter/form must contain approval of the designated investigator, the protocol (identifying protocol title and version number), and of the patient informed consent.

Any modifications made to the protocol must be submitted to the appropriate Ethic Committee for information or approval in accordance with local procedures and regulatory requirements and to Health Authorities if required.

Once approved or acknowledged by the appropriate ERB/IRB and by the Health Authorities (if required), the investigator shall implement the protocol modifications.

If applicable, in addition to the approval of the Ethics Committee according to national legislation, the protocol, other protocol related documents including patient information and informed consent and other documents as required locally must be submitted to and be approved by the health authority.

18.2. Informed consent

Informed consent for each patient will be obtained prior to initiating any trial procedures in accordance with the "Patient Information and Informed Consent". Once signed and dated, a copy of the informed consent must be given to each patient and the original copy must be retained in the investigator's site file. The informed consent form must be available in the case of data audits.

The "Declaration of Helsinki" recommends that consent be obtained from each potential patient in biomedical research trials after the aims, methods, anticipated benefits, and potential hazards of the trial, and discomfort it may entail, are explained to the individual by the physician. The potential patient should also be informed of her/his right to not participate or to withdraw from the trial at any time. The patient should be told that material from her/his tumor and blood and serum samples will be stored and potentially used for additional studies not described in this protocol.

If the patient is in a dependent relationship to the physician or gives consent under duress, the informed consent should be obtained by an independent physician. It is preferable that the patient who gives the consent signs the form but if it is not possible or if the patient is legally incompetent (i.e., a minor, or mentally incompetent), informed consent must be obtained from the parent, legal guardian, or legal representative in accordance with the law of the country in which the trial is to take place.

By signing this protocol, the investigator agrees to conduct the trial in accordance with Good Clinical Practice and the "Declaration of Helsinki".

The template Patient Information Sheet and Informed Consent has been written according to ICH guidelines which state the Informed Consent should adhere to GCP and to the ethical principles that have origin in the "Declaration of Helsinki".

19. Governance and administrative issues

